7.3 A composite cumulative endpoint of ventricular arrhythmia load

This is defined as the number of sustained ventricular tachycardia, and/or ventricular fibrillation, and/or tachycardia pacing (ATP) and/or delivery of shock therapy. All the four parameters will be captured on ICD or CRTD/P device interrogation. Sustained VT and NSVT will be captured as a backup information (in case of ICD or CRTD/P malfunction) on Holter ECG. The device will be activated during the whole study period. The Holter ECG device of 24 h' will be performed In the case of device malfunction, counter malfunction or any other cause of inability to readout the device PVC counter measurement. Holter

assessment will be conducted at one of the last 7 days of the period assessed. Data from study device/Holter will be captured on the CRF at visits 2, 3 and 5.

7.4 NT-Pro-BNP

NT-Pro-BNP Is a plasma level of B-type Natriuretic Peptide used as a blood test for diagnosing and evaluation the presence/severity of heart failure. Plasma level will be performed at visits:2 to 5.

7.5 Left ventricular end diastolic diameter

End diastolic diameter is defined as the cross-sectional diameter of the left ventricle, including the septum and the posterior thicknesses in diastole. The assessment is performed by echocardiography done at visits: 1 to 3 and 5.

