
Safety:
	
NT-Pro-BNP: NT-Pro-BNP Is a plasma level of B-type Natriuretic Peptide used as a blood test for diagnosing and evaluating the presence/severity of heart failure. Plasma level will be performed at visits: 2 to 5.
 
Left ventricular end diastolic diameter: Left ventricular end diastolic diameter is defined as the cross-sectional diameter of the left ventricle, including the septum and the posterior thicknesses in diastole. The assessment is performed by echocardiography done at visits: 1 to 3 and 5.
 
Ejection fraction: Ejection fraction is defined as the ratio of the stroke volume to the end-diastolic volume in the left ventricle as performed by echocardiography and expressed by percentage. The assessment is performed by echocardiography done at visits: 1 to 3 and 5.
 
The following evaluations will be conducted to assess the safety of the treatment regimens:
 
 Adverse events Clinical laboratory evaluations (hematology, biochemistry, urine analysis) Complete physical examination including vital signs. Concomitant medication and procedures

Sample size consideration
	
The planned sample size is 128 subjects, 64 in each study arm. When the sample size in each sequence group is 64, (a total sample size of 128) a 2 x 2 crossover design will have 80% power to detect a difference in Mean reduction of -10.0, assuming that the Crossover ANOVA MSE is 28.284 (the Standard deviation of differences, sd, is 40.0) using a two group T-test (Crossover ANOVA) with a 0.05 two-sided significance level.

Efficacy analysis:
	
The primary efficacy is the percentage of PVCs during the 2 months of empagliflozin treatment compared with the percentage of PVC on placebo. The two-sample T-test or Non-parametric Wilcoxon-Mann-Whitney Rank sum test for independent samples (as is appropriate) will be applied for testing the carry-over effect in the primary endpoint between the two sequences.
 
If no carry-over effect will be observed, then The Paired T-test or non-parametric Signed-rank test for two means (as is appropriate) will be applied for analyzing the difference in the above changes between the tested treatment and placebo.

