3.2 Secondary Objectives

To evaluate the effect of Empagliflozin on cardiac function, using molecular (NT-Pro_BNP levels), echocardiographic and physiological markers of myocardial function.

4 Trial Design

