4.1.2 Secondary Endpoints

1. The number of non-sustained ventricular tachycardia (NSVT) episodes, defined as the NSVT number in a pre-specified period captured on ICD or CRTD/P device.
2. A composite cumulative endpoint of ventricular arrhythmia load (number of: sustained ventricular tachycardia, ventricular fibrillation, antitachycardia pacing (ATP) or delivery of shock therapy episodes, defined as the arrhythmias number in a pre-specified period captured on ICD or CRTD/P device.
3. The change in blood level of NT-Pro Brain Natriuretic peptide (BNP) from baseline to the end of any of the treatment periods
4. The change in Left ventricular end diastolic diameter on echocardiography from baseline to the end of any of the treatment periods.
5. The change in Left ventricular ejection fraction (EF) on echocardiography from baseline to the end of any of the treatment periods.
6. Safety.

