7.6 Left ventricular ejection fraction (EF)

Ejection fraction is defined as the ratio of the stroke volume to the end-diastolic volume in the left ventricle as performed by echocardiography and expressed by percentage. The assessment is performed by echocardiography done at visits: 1 to 3 and 5.

8 Assessment of Safety

Safety assessments will consist of evaluating adverse events and serious adverse events, adverse events of special interest, laboratory parameters including hematology, chemistry & urine analysis, vital signs, physical examinations, monitoring compliance, and documentation of all concomitant medications and/or therapies.

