Frequency of non-sustained ventricular tachycardia (NSVT) episodes and composite cumulative ventricular arrhythmia load will be summarized by treatment.

Changes in blood level of NT-Pro Brain Natriuretic peptide (BNP), Left ventricular end diastolic diameter and Left ventricular ejection fraction (EF) from baseline will be summarized in appropriate tables by treatment.

9.2.2 Safety Analysis:

Data from all subjects who receive any study drug will be included in the safety analyses.

All adverse events will be coded using the Medical Dictionary for Regulatory Activities (MedDRA, most updated Version) terminology and presented in tables by System Organ Class (SOC) and Preferred Term (PT).

AE data will be listed individually and summarized by SOC and by PT within a system organ class under each treatment.

The severity of the toxicities will be graded according to the NCI CTCAE (Ver4.0) whenever possible. In the by-subject analysis, a subject having the same event more than once will be counted only once. Adverse events will be summarized by worst NCI CTC grade. Adverse events leading to death or to discontinuation from treatment, events classified as NCI CTCAE Grade 3 or Grade 4, study-drug-related events, and serious adverse events will be summarized separately.

Laboratory data will be graded according to NCI CTCAE severity grade.

Any deviations from the previously described statistical plan will be described and justified in a protocol amendment.

Other safety parameters including vital signs and physical examination will be summarized in appropriate tables.

Concomitant medications entered into the database will be coded using the World Health Organization (WHO) Drug Reference List, which employs the Anatomical Therapeutic Chemical classification system.

10 Direct Access to Source Data/Documents

Access to the subject's source data and study documents will occur only with the subject's acknowledgement and agreement by signing an informed consent. The investigator will permit study-related monitoring, audits, Institutional Review Board (IRB) review and regulatory inspection(s), providing direct access to source data and documents.

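### The written definition of LV end-diastolic diameter adds both walls to the cavity, so change in secondary endpoint 4 mixes wall change with chamber change (wrong as written, minor)

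*Combined protocol and SAP*

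**What the plan says.** Section 4.1.2 lists as secondary endpoint 4: "The change in Left ventricular end diastolic diameter on echocardiography from baseline to the end of any of the treatment periods". It does not say how the diameter is measured, and neither does the endpoint list in the synopsis.

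The measurement is defined in two places. Section 7.5 defines it as the "cross-sectional diameter of the left ventricle, including the septum and the posterior thicknesses in diastole" and places the echocardiograms at visits 1 to 3 and 5. The synopsis (Assessments) gives the same definition: "Left ventricular end diastolic diameter is defined as the cross-sectional diameter of the left ventricle, including the septum and the posterior thicknesses in diastole".

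The endpoint serves the secondary objective in section 3.2: "To evaluate the effect of Empagliflozin on cardiac function, using molecular (NT-Pro_BNP levels), echocardiographic and physiological markers of myocardial function". For the analysis, section 9.2.1 says that changes in NT-proBNP, LVEDD and ejection fraction "from baseline will be summarized in appropriate tables by treatment". No hypothesis test is assigned to LVEDD there.

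**The concern.** An end-diastolic diameter is ordinarily a cavity dimension, taken between the endocardial surfaces of the septum and the posterior wall. The written rule brings both walls inside the measurement. A site that follows the text would report cavity plus walls under a name that readers will take to mean the cavity.

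What is at stake is interpretation. The endpoint is there to show whether the drug affects cardiac function, and the natural reading of a smaller LVEDD is a smaller chamber. Under the written rule, a smaller value could come from the chamber, from the walls, or from both. A true chamber change could also be partly or wholly hidden by wall change in the opposite direction.

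**Working it through.** **Text check.** The two definitions were compared with every other mention of the endpoint.

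| Place | What it gives |
|---|---|
| Synopsis, secondary endpoints | Names the endpoint; no measurement rule |
| Synopsis, Assessments | Diameter "including the septum and the posterior thicknesses in diastole" |
| Section 4.1.2 | Names the endpoint; no measurement rule |
| Section 7, opening list | Names the endpoint; no measurement rule |
| Section 7.5 | Same definition as the synopsis |
| Section 9.2.1 | Descriptive summary by treatment |

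The two definitions agree, so this is the protocol's settled wording and not a slip in one place. No section says that an internal dimension is meant, and none lists septal or posterior wall thickness as a variable. The visit procedures in section 4.2.2 mention echocardiography only in connection with ejection fraction and give no reading rule for the diameter.

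**Arithmetic.** The plan states no figure that depends on this definition, so there is none to reproduce. Let s be septal thickness, c the cavity diameter and p posterior wall thickness, all at end diastole. By the wording:

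- Endpoint value: E = s + c + p
- Change from baseline: ΔE = Δs + Δc + Δp

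Two consequences follow.

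1. If the walls do not change (Δs = Δp = 0), then ΔE = Δc. The level of E is higher than the cavity diameter, but the change is the same.
2. If the walls change, ΔE departs from Δc by exactly Δs + Δp.

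Illustration with assumed changes (the documents give none), the same change in each wall:

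| Cavity change, mm | Change in each wall, mm | Endpoint change, mm |
|---|---|---|
| −2 | −0.5 | −2 + 2(−0.5) = −3 |
| −2 | 0 | −2 + 2(0) = −2 |
| −2 | +0.5 | −2 + 2(+0.5) = −1 |
| −2 | +1 | −2 + 2(+1) = 0 |
| 0 | −1 | 0 + 2(−1) = −2 |

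The second and last rows give the same endpoint change from different causes. In the fourth row, a real cavity change disappears.

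**Reach.** The sample size in section 9.1 rests on a difference of 10 and a standard deviation of differences of 40 for the arrhythmia endpoint. LVEDD does not enter it. Eligibility in section 5.1 uses ejection fraction, not LVEDD.

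**The case against.** The strongest reply has three parts.

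*The endpoint is a within-patient change, so the walls cancel.* This stands where the walls are constant and the rule is applied uniformly. A reader might infer that, because the written quantity is larger than the cavity diameter, the endpoint is biased. It is not biased for that reason: a constant offset drops out of the change. What remains is wall change during the study, and the documents say nothing about how large that would be.

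*The sentence may only mean that wall thicknesses are recorded alongside the diameter, and sonographers will measure the cavity anyway.* Either may be true. But the sentence does not say the first, and no section lists the thicknesses as variables. If the second is true, sites would be departing from the written definition. The same edit settles both.

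*The stakes are low.* This stands. LVEDD is one secondary endpoint, it is summarized descriptively, and no test, alpha or power attaches to it.

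Two further inferences are tempting and not supported. A reader might infer that mixing conventions between visits will produce large false changes. That needs a reader to depart from the single rule that the protocol gives in both places, so it is conjecture about adherence and not a defect in the rule. A reader might also infer a contradiction with section 7.6, where ejection fraction is the "ratio of the stroke volume to the end-diastolic volume in the left ventricle". There is none: a linear dimension and a ratio of volumes are different quantities under any definition of the diameter.

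**Conclusion.** The definition is wrong as written, with minor severity. Taken literally, secondary endpoint 4 is an outer dimension, and its change is the sum of chamber change and wall change. Each 1 mm of change in both walls contributes 2 mm. That figure is arithmetic from the wording; the millimetre values in the illustration are assumptions.

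The conclusion rests on the literal reading and on the absence of any correcting text. It does not show that the endpoint would in fact be biased, or by how much. A reader might want to set the 2 mm against an expected drug effect on LVEDD, but the documents state no such effect, so that comparison cannot be made. Section 2.6 says that the drug contracts intravascular volume, and a reader might infer that the walls would thicken as the cavity shrinks, so that the endpoint would systematically understate chamber change. The documents give no wall or cavity dimensions, and nothing on wall behaviour, to support that.

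The primary endpoint, the sample size and the type I error rate are unaffected.

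**What to change.** In section 7.5 and the synopsis, define LVEDD as the internal left ventricular diameter at end diastole, from septal endocardium to posterior wall endocardium, excluding both walls. Carry the same wording into any echo worksheet. State that one convention applies at every echocardiogram used for the endpoint, that is visits 1 to 3 and 5 as section 7.5 lists them. If septal and posterior wall thicknesses are of interest, name them as separate variables and summarize them separately.

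The cost is one corrected definition in two places of the protocol, plus the worksheet. It needs no extra visit or imaging and no change to the analysis in section 9.2.1.

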7.6 Left ventricular ejection fraction (EF)

Ejection fraction is defined as the ratio of the stroke volume to the end-diastolic volume in the left ventricle as performed by echocardiography and expressed by percentage. The assessment is performed by echocardiography done at visits: 1 to 3 and 5.

8 Assessment of Safety

Safety assessments will consist of evaluating adverse events and serious adverse events, adverse events of special interest, laboratory parameters including hematology, chemistry & urine analysis, vital signs, physical examinations, monitoring compliance, and documentation of all concomitant medications and/or therapies.

8.1 Adverse events

The information obtained during study visit subject questioning, review of subject's compliance record, physical examinations, vital signs measurements, blood testing, and by any other means will be evaluated in light of baseline medical data and thus provide the basis for adverse events identification and grading. The adverse events reported during the trial will be graded (see [8.1.3 below](#)), documented and assessed in light of their clinical significance and relation to investigational product. In addition, the following information regarding the AE must be obtained: start date, end date (if applicable), outcome (resolved / unresolved), and action taken (e.g. dose adjustment, therapy discontinuation, concomitant medication). Adverse event monitoring will be conducted throughout subject's participation.

Information about all adverse events, whether volunteered by the patient, discovered by investigator questioning, or detected through physical examination, laboratory test or other means, will be collected and recorded on the Adverse Event Case Report Form and followed as appropriate.

Medical conditions/diseases present before starting study treatment are only considered adverse events if they worsen after starting study treatment.

Clinical events occurring before starting study treatment but after signing the informed consent form are recorded on the Medical History/Current Medical Conditions Case Report Form. Abnormal laboratory values or test results constitute adverse events only if they induce clinical signs or symptoms leading to a premature control of the abnormal value before the next scheduled laboratory test, leading to a change in study medication (e.g. dose

modification, interruption or permanent discontinuation), requires a change in concomitant therapy (e.g. addition or change in a concomitant medication, therapy or treatment) or require therapy.

Any Adverse Event occurring by the time of study completion (within four weeks of last drug intake) must be recorded on the Adverse Event CRF page.

Any adverse event term needs to be provided for each event; preferably using the short name based on the CTCAE ver. 4.0 or preferred term on the MedDRA.

8.1.1 Definitions of adverse events

Adverse event

An adverse event is defined as any untoward medical occurrence or effect in a patient treated on a study protocol, which does not necessarily have a causal relationship with the study treatment. An AE is therefore described as any unfavorable and unintended sign (including an abnormal laboratory finding), symptom or disease temporally associated with the use of the study treatment, whether or not considered related to the study treatment. This definition includes any abnormalities or anomalies that were not seen at baseline or which worsened during the course of the study, if present at baseline.

Adverse Reaction (AR)

This is defined as **all untoward and unintended responses to a study treatment related to any dose administered**. A causal relationship between the study treatment and an AE is at least a reasonable possibility (probably or possibly related), i.e. the relationship cannot be ruled out.

Serious Adverse Event

A serious AE (SAE) is defined as any AE occurring at any dose that results in any of the following outcomes:

- death
- a life-threatening AE, as defined below
- patient hospitalization or prolongation of existing hospitalization
- a persistent or significant disability/incapacity

- a congenital anomaly/birth defect
- important medical event, as defined below

A life-threatening AE is any AE that places the subject, in the view of the investigator, at immediate risk of death from the reaction as it occurred (i.e. it does not include a reaction that, had it occurred in a more severe form, might have caused death).

An important medical event is an AE that may not result in death, be life-threatening, or require hospitalization but may be considered a serious AE when, based upon appropriate medical judgment, may jeopardize the subject and may require medical or surgical intervention to prevent one of the outcomes listed above. It can also include AEs otherwise judged to be serious by either the investigator or the sponsor.

8.1.2 Adverse events of Special Interest (AESIs)

The term AESI relates to any specific AE that has been identified at the project level as being of particular concern for prospective safety monitoring and safety assessment within this trial, e.g. the potential for AEs based on knowledge from other compounds in the same class. AESIs need to be reported to the Pharmacovigilance Department of Boehringer Ingelheim within the same timeframe that applies to SAEs.

Patients with AESIs need to be followed up appropriately, regardless of the origin of the laboratory data (e.g. central, local etc.). The Investigator should consider which, if any, concomitant therapies should not be taken during evaluation. Discontinued treatments can be reintroduced per Investigator discretion.

The following are considered as AESIs:

Hepatic injury

A hepatic injury is defined by the following alterations of hepatic laboratory parameters after randomisation:

- an elevation of AST and/or ALT ≥ 3 fold ULN combined with an elevation of total bilirubin ≥ 2 fold ULN measured in the same blood sample
- an isolated elevation of ALT and/or AST ≥ 5 fold ULN

These laboratory findings constitute a hepatic injury alert and the patients showing these abnormalities need to be followed up according to medical judgement. .

In case of clinical symptoms of hepatic injury (icterus, unexplained encephalopathy, unexplained coagulopathy, right upper quadrant abdominal pain, etc.) without laboratory results (ALT, AST, total bilirubin) available, the Investigator should make sure these parameters are analysed, if necessary in an unscheduled blood test.

Decreased renal function

Decreased renal function is defined by a creatinine value showing a ≥ 2 fold increase from baseline and is above the ULN.

For the AESI “decreased renal function”, the Investigator shall collect an unscheduled laboratory sample for creatinine as soon as possible and initiate follow-up laboratory tests of creatinine according to medical judgement.

Metabolic acidosis, ketoacidosis and diabetic ketoacidosis (DKA)

In case of metabolic acidosis, ketoacidosis and DKA further investigations should be done according to the medical judgment and the clinical course until a diagnosis is made and/or the patient is recovered.

DKA is defined by the diagnostic criteria in the table below, and as defined by the American Diabetes Association (ADA).

Investigators should note that not all criteria in the table below need to apply for the diagnosis of DKA, and clinical judgment should also be taken into consideration. Due to its mechanism of action, empagliflozin may potentially modify the clinical presentation of DKA which may occur at lower plasma glucose levels than stated in the table below.

Table 3 Diagnostic criteria for DKA

Table 3 Diagnostic criteria for DKA

	DKA		
	Mild	Moderate	Severe

Plasma glucose (mg/dL)	>250	>250	>250
Arterial pH	7.25-7.30	7.00-7.24	<7.00
Serum bicarbonate (mEq/L)	15-18	10 to <15	<10
Urine ketones*	Positive	Positive	Positive
Serum ketones*	Positive	Positive	Positive
Effective serum osmolality (mOsm/kg)**	Variable	Variable	Variable
Anion gap***	>10	>12	>12
Alteration in sensoria or mental obtundation	Alert	Alert/drowsy	Stupor/coma

* Nitroprusside reaction method

** Calculation: $2[\text{measured Na (mEq/L)} + \text{gluc}]$

Contact details of the local pharmacovigilance unit/LVPM: E-mail: PV_local

[contact]

Suspected Unexpected Serious Adverse Reaction (SUSAR) This is defined as an adverse reaction, the nature or severity of which is not consistent with the known study treatment information.

8.1.3 Adverse events grading

AE will be documented and graded according to the International Common Toxicity Criteria (CTCAE) version 4.0

AE that do not appear in the CTC will be graded as follows:

- Mild (Grade 1): Sign or symptom, usually transient, requiring no special treatment and generally not interfering with usual activities
- Moderate (Grade 2): Sign or symptom, which may be ameliorated by simple therapeutic measures, may interfere with usual activity.
- Severe (Grade 3): Sign or symptom that is intense or debilitating and that interferes with usual activities and/or requires hospitalization. Recovery is usually aided by therapeutic measures and the discontinuation of the study product may be required.

- Life threatening or disabling (Grade 4): Sign or symptom that is Life threatening or disabling.
- Death (Grade 5): Death related to AE

